5.6 Screen Failures

Screen failures are defined as subjects who consent to participate in the clinical study but are not subsequently randomized. To ensure transparent reporting of screen failure subjects, a minimal set of screen failure information will be collected, including demography, reason for screen failure (e.g. withdrawal of consent), eligibility criteria, any protocol deviations and any adverse events or incidents as applicable.

Individuals who do not meet the criteria for participation in this study (screen failure) may not be re-screened.

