8.1.9 Dispense Wash-out Products and Diary Cards

Subjects will be dispensed with the washout toothbrush and the 0ppm fluoride washout dentifrice to use during the washout period. Subjects will be instructed to brush their teeth with the 0ppm fluoride washout dentifrice twice a day during the 2 days prior to Visit 2, 4 and 6 (including the morning of the treatment visit) and record it in the diary provided.

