10.3 Time Period and Frequency for Collecting AE and SAE Information

All AEs, and therefore all SAEs will be collected immediately after a subject provides consent to participate in the study by the completion (signature) of the ICF and until 5 days following last administration of the study product (or last procedure).

Medical occurrences that began before obtaining informed consent will be recorded in the Medical History/Current Medical Conditions section of the CRF not the AE section.

Details recorded by the subject on a diary or similar document that meet the definition of an AE must also be discussed with the subjects and transcribed in the AE section of the CRF.

All SAEs will be recorded and reported to the sponsor or designee immediately and under no circumstance should this exceed 24 hours. The investigator will submit any updated SAE data to the sponsor within 24 hours of it being available.

Investigators are not obligated to actively seek AEs or SAEs after the conclusion of the study participation. However, if the investigator learns of any SAE, including a death, at any time

Property of Haleon- Confidential

May not be used, divulged, published or otherwise disclosed without the consent of Haleon

after a subject has been discharged from the study, and he/she considers the event to be reasonably related to the study product or study participation, the investigator must promptly notify the sponsor.

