12.3.4 Safety Analyses

AEs will be regarded as treatment emergent if they occur on or after the first use of study product in the study. In this crossover trial, events will be assigned to the study product being received at the onset of the event. Treatment-emergent adverse events (TEAEs) with an onset date/time between visits will be assigned to the study product received in the previous period. TEAEs with an onset after last use of any study product will be assigned to the last study product used.

The number of distinct events and the number and percentage of subjects having at least one event will be presented by study product and overall for the following:

- AEs (overall only)
- SAEs (overall only)
- TEAEs
- Serious TEAEs
- Oral TEAEs
- Product Related TEAEs
- Device related AEs
- Device Incidents

All AEs and device incidents will be listed providing all relevant details collected in the CRF.

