3.2 Timepoints and Visit Windows

Visits and assessments will be conducted in line with the Schedule of Activities (section 1.1) and any which are out-of-window will be recorded as protocol deviations and assessed for exclusion from the Per-Protocol (PP) Population (section 4.1.2). Otherwise, the results from each scheduled visit and assessment will directly represent the result at the respective time-point in all analyses.

4 Data Analysis

Data analysis will be performed by the **CCI** **CCI**. The statistical analysis software used will be SAS version 9.4 in Windows environment.

Prior to database closure a Blind Data Review Meeting (BDRM) will be conducted in which various aspects of the trial will be discussed and agreed.

Except as described below, all listings will be produced for all randomized subjects.

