16.2.7 Adverse event listings				
Listing	16.2.7.1	Adverse Events	ITT Population	
Listing	16.2.7.2	Device Incidents	ITT Population	

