ID	Visit Dates	Treatment Sequence Group	Date of PD	Protocol Deviation (PD)	Important PD	Important PD affect efficacy and Visit data exclusion from PP analysis
	V1: Date 1 V2: Date 2 V3: Date 3 V4: Date 4 V5: Date 5 V6: Date 6 V7: Date 7	ABC	DDMMYYYY	xxxxxxxxxxxxxx	Yes or No	Yes or No, Vx

A = Test, B = Reference, C= Placebo

PP = Per-Protocol

Haleon Confidential

CCI

Statistical Analysis Plan Template v7.0

Page 40 of 43

Listing 16.2.3, Exclusions from Efficacy Analysis, ITT Population

ID	Treatment Sequence Group	Study Periods Excluded from PP analysis	Reason for Exclusion
	ABC	P1/P2/P3	XXXXXXXXXXXXXXXXXXXX

A = Test, B = Reference, C= Placebo

Haleon Confidential

CCI

Statistical Analysis Plan Template v7.0

Page 41 of 43

Listing 16.2.7.1, Adverse Events, ITT Population

ID	Visit Dates	Treatment Sequence Group	AE Description	AE Dates Start-Stop	TEAE / Last Study Product Used	Serious/ Severity / Related to Study Product / Oral	Frequency/ Outcome/ Action/ Withdraw from study
	V1: Date 1 V2: Date 2 V3: Date 3 V4: Date 4 V5: Date 5 V6: Date 6 V7: Date 7	ABC	xxxxxxxxxxxxxxxxxxxx	DDMMYYYY- DDMMYYYY	Yes or No, A	Serious or Not Serious / Mild or Moderate or Severe / Related or Not Related / Oral or Not Oral	Xxxx/ Xxxx/ Xxxx/ Yes or No

A = Test, B = Reference, C= Placebo

Haleon Confidential

CCI

Statistical Analysis Plan Template v7.0

Page 42 of 43

Listing 16.2.7.2, Device Incidents, Non-Randomized Subjects

ID	Visit Dates	Treatment Sequence Group	Incident Date	Incident Description	Incident related to AE
	V1: Date 1 V2: Date 2 V3: Date 3 V4: Date 4 V5: Date 5 V6: Date 6 V7: Date 7	ABC	DDMMYYYY	XXXXXXXXXXXXXXXXXX	Yes or No

A = Test, B = Reference, C= Placebo

Haleon Confidential

CCI

Statistical Analysis Plan Template v7.0

Page 43 of 43

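### Adverse events in consented, never-randomized subjects reach no planned SAP output, and the device-incident listing is given two mutually exclusive populations

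*SAP*

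**What the plan says.** **Collection.** Protocol 10.3 starts the reporting period at the consent signature: "All AEs, and therefore all SAEs will be collected immediately after a subject provides consent to participate in the study". Protocol 5.6 defines screen failures as subjects who consent but are not later randomized, and includes among the data kept for them "any protocol deviations and any adverse events or incidents as applicable".

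**Commitment.** Protocol 12.3.4 states: "All AEs and device incidents will be listed providing all relevant details collected in the CRF". SAP 4.5 repeats the sentence. Neither document attaches a population to it.

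**Outputs.** The opening of SAP Section 4 sets the default: "Except as described below, all listings will be produced for all randomized subjects". The shell for the AE listing is headed "Listing 16.2.7.1, Adverse Events, ITT Population", and Appendix 4 gives the same population. Appendix 4 also has an entry 16.2.7.2, titled "Device Incidents", with ITT as its population, whereas the shell for that number reads "Listing 16.2.7.2, Device Incidents, Non-Randomized Subjects". Table 14.3.1, the only table of AEs and device incidents, is on the Safety population. SAP 4.1.3 defines ITT as everyone randomized, and Safety as everyone randomized who received at least one dose. SAP Section 5 declares no change from the protocol's planned analysis.

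**The concern.** Collection begins at consent, but every AE output begins at randomization or first dose, so subjects who stop in between have nowhere to be reported.

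That interval involves exposure. Eligible subjects leave Visit 1 with a washout dentifrice and a toothbrush, and are told to "brush their teeth with the 0ppm fluoride washout dentifrice twice a day during the 2 days prior to Visit 2, 4 and 6". Protocol 10.1 counts events associated with a washout product or a device as AEs, and Protocol 10.10 names the supplied toothbrush as the medical device. At Visit 2 (Protocol 8.2.1) the AE enquiry, soft-tissue examination, diary review and continuance decision all precede randomization. A reaction to the washout paste is thus elicited just before the step at which it could stop the subject from being randomized. If it does, the event is missing from the study report's displays even if it is serious.

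For device incidents, the two population labels for one listing exclude each other, so a programmer has to choose, and either choice leaves out incidents that both documents undertake to list.

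**Working it through.** No arithmetic applies. The check follows each kind of event through the planned displays.

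**Inputs**
- AE listing 16.2.7.1: ITT (SAP Appendices 4 and 5 agree).
- Device-incident listing 16.2.7.2: ITT (Appendix 4) or non-randomized subjects (Appendix 5).
- Table 14.3.1: Safety population.
- Subject disposition listing 16.2.1: Screened population, but its shell has no AE or incident field. Its reason-for-discontinuation column could at most show that an event was the reason for stopping.

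**Trace for AEs and SAEs**

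| Subject | Listing 16.2.7.1 | Table 14.3.1 | Result |
|---|---|---|---|
| Consented, never randomized | No | No | In no output |
| Randomized, not dosed | Yes | No | Listed |
| Randomized and dosed | Yes | Yes | Listed and counted |

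**Trace for device incidents**

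| Subject | 16.2.7.2 as in Appendix 4 | 16.2.7.2 as in the shell | Table 14.3.1 |
|---|---|---|---|
| Consented, never randomized | Not listed | Listed | Not counted |
| Randomized, not dosed | Listed | Not listed | Not counted |
| Randomized and dosed | Listed | Not listed | Counted |

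**Reading the tables**
1. The gap for AEs does not depend on any choice of reading, because both appendices agree on ITT.
2. Under Appendix 4, incidents in never-randomized subjects are in no output.
3. Under the shell, incidents in randomized subjects are unlisted. Those in dosed subjects remain as counts in Table 14.3.1; those in randomized but undosed subjects are in no output.
4. The shell is also inconsistent within itself. It has a treatment-sequence column with ABC as the example entry, which a non-randomized subject could not fill.

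**The case against.** **The SAP text may already cover the gap.** The default sentence in Section 4 allows for exceptions described later, and SAP 4.5, which comes later, promises a listing of all events. On that reading the SAP text matches the protocol and the fault lies in the appendices. This is a fair reading, but the displays are specified in the appendices, and both restrict the AE listing to ITT. Whichever part governs, the other must change.

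**The device shell title looks like a slip.** Appendix 4, the Section 4 default and the shell's own columns all point to randomized subjects. That is probably right. But correcting the title to ITT would only move the loss to incidents in non-randomized subjects.

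**A reader might infer that device incidents in treated subjects vanish altogether, or that both device losses occur together.** The documents support neither. Table 14.3.1 still counts incidents in dosed subjects, and the two losses require opposite readings of the same listing.

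**The consequence is limited.** This stands. The safety endpoint is treatment-emergent AEs, which begin at first use of study product, so a never-randomized subject cannot contribute one. Washout reactions in subjects who go on to be randomized are in Listing 16.2.7.1. Under the order in Protocol 8.1, eligibility is settled before washout products are dispensed, so only subjects who pass screening and then drop out before randomization have the washout exposure. SAEs and device incidents go to the sponsor within 24 hours under Protocol 10.3 and 10.11, whatever the listings contain.

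**Conclusion.** The point holds as a break between the plan's commitment and its specified outputs. AEs and SAEs in consented, never-randomized subjects are collected and promised for listing, yet are assigned to no display. Listing 16.2.7.2 carries two populations that cannot both be right, and neither alone meets the commitment.

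The size cannot be given. The documents do not state how many subjects will consent without being randomized, or how many of those will have used the washout products; the number may be small. What is affected is the completeness of safety reporting. A reader might go on to infer a biased tolerability comparison between dentifrices, or a fault in Table 14.3.1. Neither follows: the comparison rests on events after first dose, and the table is correct for the population that it names.

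The conclusion assumes that outputs will be programmed as Appendices 4 and 5 specify.

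**What to change.** - Produce Listings 16.2.7.1 and 16.2.7.2 for the Screened population, which contains every consented subject and already serves Listing 16.2.1. Enter *not randomized* in the sequence column where it applies. Paired listings, one for randomized and one for non-randomized subjects, would do equally well.
- Make the Appendix 4 entries and the Appendix 5 shell titles agree with that choice.
- Amend the default sentence at the start of SAP Section 4 to name these listings as exceptions.
- Leave Table 14.3.1 as it is. Its percentages are defined on the Safety population, and the listings alone meet the commitment.

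The cost is a few lines of SAP wording and a changed population filter in two listings. No new data are needed, since Protocol 11.1 requires a case report form for every consented subject. The change can be made before database lock.
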